#### **10.8 Sample Size Calculation**

The 6-month CR rate will be estimated with a one-sided 90% confidence interval of Agresti-Coull type with the lower bound to be calculated and the upper bound set as 1. With an expected CR rate of  $\geq 25\%$ , a sample size of 20 patients will have a power of 0.80 to exclude a lower bound being  $\leq 10\%$ .

Using a conservative estimate of FGFR3 mutation or over-expression present in 40% of BCG-refractory tumors, 50 patients will need to be screened in order to enroll the required 20 patients on dovitinib therapy.

The estimated accrual duration is 12 months and the estimated overall study duration is 2 years.

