STATISTICAL CONSIDERATIONS	
General Considerations
 
Statistical analysis of this study will be the responsibility of the Department of Biostatistics at IUSM. Parameter estimates and relevant summary statistics will be reported for both efficacy and safety outcomes. Continuous variables will be summarized by means, medians, minima, maxima and standard deviations. Categorical variables will be summarized by frequencies and percentages. Missing data are expected to be rare. For patients that start therapy but do not make it to the primary endpoint evaluation, their 6-month status will be treated as not achieving CR. Consequently, our estimate of 6-month CR rate will be conservative. For secondary outcomes, missing data, if any, will not be imputed and complete-case analysis will be adopted. Additional exploratory analysis will be conducted when appropriate. Changes from the analysis plan will not require an amendment to the protocol unless it changes a significant feature in the protocol.
 
Primary Objective Statistical Considerations
 
The 6-month complete response rate will be summarized by frequency and rate. The one-sided 90% confidence interval (CI) of Agresti-Coull type will be calculated for the rate.
 
Secondary Objectives Statistical Considerations
 
All secondary objectives are hypothesis generating in nature. One year RFS will be summarized by mean, median and standard deviation. Muscle-invasive progression, 3-

	
and 6-month PR, and toxicity rates will be presented as rates and corresponding 90% Agresti-Coull CIs.
 
Sample size justification
 
A one-sided 90% confidence interval (CI) of Agresti-Coull type will be calculated for the 6-month CR rate. With an expected CR rate of <math>\geq 25\%</math>, a sample size of 20 subjects will have a power of 0.80 to exclude a lower bound being <math>\leq 10\%</math>.

ENROLLMENT PERIOD	18 months
FOLLOW-UP PERIOD	6 months

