## SCHEMA

Phase II Trial of Dovitinib in BCG-Refractory Urothelial Carcinoma Patients with Tumor FGFR3 Mutations or Over-expression: Hoosier Cancer Research Network GU12-157

- Assessments
  - SOC Cystoscopy, urine cytology, TURBT q3month
  - CBC, CMP, toxicity assessment qMonth
- Key Stats
  - The 6-month CR rate will be estimated with a one-sided 90% confidence interval of Agresti-Coull type. With an expected CR rate of  $\geq 25\%$ , a sample size of 20 patients will have a power of 0.80 to exclude a lower bound being  $\leq 10\%$ .
- Key Eligibility
  - Failure to achieve CR within 6 mo of initial BCG or recurrence within 12 mo of CR from prior BCG
  - FGFR3 mutation accessed by massively parallel sequencing analysis using the Ion Torrent PGM instrument or over-expression by IHC
  - Medically unfit to undergo cystectomy or willing to forego cystectomy
  - ECOG PS 0-2
  - No concurrent upper tract tumors

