## **10 Statistical Methods and Data Analysis**

### **10.1 General Considerations**

Statistical analysis of this study will be the responsibility of the Department of Biostatistics at IUSM. Parameter estimates and relevant summary statistics will be reported for both efficacy and safety outcomes. Continuous variables will be summarized by means, medians, minima, maxima and standard deviations. Categorical variables will be summarized by frequencies and percentages. Missing data are expected to be rare. For patients that start therapy but do not make it to the primary endpoint evaluation, their 6-month status will be treated as not achieving CR. Consequently, our estimate of 6-month CR rate will be conservative. For secondary outcomes, missing data, if any, will not be imputed and complete-case analysis will be adopted. Additional exploratory analysis will be conducted when appropriate. Changes from the analysis plan will not require an amendment to the protocol unless it changes a significant feature in the protocol.

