#### **10.5.1 Primary Objective Statistical Considerations**

The 6-month complete response rate will be summarized by frequency and rate. The one-sided 90% confidence interval (CI) of Agresti-Coull type will be calculated for the rate.

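### The stated power of 0.80 with 20 patients is 0.77 under the plan's own one-sided 90% Agresti-Coull bound at a true CR rate of 25%

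*Combined protocol and SAP*

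**What the plan says.** Section 10.8 (Sample Size Calculation) defines the primary analysis interval as a "one-sided 90% confidence interval of Agresti-Coull type with the lower bound to be calculated and the upper bound set as 1". With an expected 6-month CR rate of at least 25%, it then claims that "a sample size of 20 patients will have a power of 0.80 to exclude a lower bound being" at or below 10%. The synopsis makes the same claim ("a sample size of 20 subjects will have a power of 0.80 to exclude a lower bound being" at or below 10%), and so does the schema under its key statistics ("a sample size of 20 patients will have a power of 0.80").

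Section 10.5.1 confirms that this interval is the one to be reported: "The one-sided 90% confidence interval (CI) of Agresti-Coull type will be calculated for the rate".

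None of these places gives a responder cut-off, a power formula, the software used or a type I error.

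**The concern.** The sample size, the rate to exclude, the expected rate and the interval are all fixed by the plan, so its power can be computed exactly. With 20 patients the number of CRs is a whole number and success reduces to a cut-off, so only a few power values are possible at a true rate of 25%. The stated 0.80 is not one of them.

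Power of 0.80 is the sole quantitative justification for enrolling 20 patients, and it appears three times. If it is overstated, readers are told the chance of missing the target at 25% is 0.20 when it is higher. They also have no figure for the opposite error, the chance of excluding 10% when the true rate is only 10%.

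**Working it through.** **Inputs**

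- n = 20 (section 10.8, synopsis, schema).
- One-sided 90% Agresti-Coull lower bound, upper bound fixed at 1 (section 10.8), so z = 1.2816.
- Rate to exclude: 10% or lower (section 10.8).
- Expected rate: 25% or higher (section 10.8). Power is evaluated at 25%, the lowest rate the statement covers.

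**Step 1: lower bound for each number of CRs, x**

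ñ = n + z² = 20 + 1.6424 = 21.642

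p̃ = (x + z²/2)/ñ = (x + 0.8212)/21.642

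L = p̃ − z·√(p̃(1 − p̃)/ñ)

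| x of 20 | p̃ | z × standard error | L |
|---|---|---|---|
| 3 | 0.1766 | 0.1050 | 0.0715 |
| 4 | 0.2228 | 0.1146 | 0.1081 |
| 5 | 0.2690 | 0.1222 | 0.1468 |

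The bound exceeds 0.10 from 4 CRs upward.

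**Step 2: exact power at 25%**

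P(X ≤ 3 | 20, 0.25) = 0.0032 + 0.0211 + 0.0669 + 0.1339 = 0.2252 (from unrounded terms)

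Power = 1 − 0.2252 = **0.7748**, against 0.80 stated.

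**Step 3: attempts to reproduce 0.80**

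The neighbouring cut-offs at 25% give 0.909 (at least 3) and 0.585 (at least 5). No method that amounts to a whole-number cut-off at n = 20 can therefore give 0.80.

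| Method | CRs needed | Exact power at 25% |
|---|---|---|
| One-sided 90% Agresti-Coull (the plan's), Wilson or Jeffreys | 4 | 0.775 |
| One-sided 90% Wald or Clopper-Pearson | 5 | 0.585 |
| Two-sided 90% Agresti-Coull, Wilson, Jeffreys or Clopper-Pearson | 5 | 0.585 |
| Two-sided 90% Wald | 6 | 0.383 |
| One-sided 90% plus-4 | 3 | 0.909 |
| Two-sided 90% plus-4 | 4 | 0.775 |

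One-sided normal-approximation formulas do not give it either:

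- Null and alternative variances: Φ((0.15 − 1.2816·√(0.10·0.90/20))/√(0.25·0.75/20)) = Φ(0.661) = 0.746.
- Null variance only: 0.830.
- Alternative variance only: 0.606.
- Arcsine: 0.700.
- Continuity-corrected approximation to P(X ≥ 4): 0.781.

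**Step 4: where 0.80 is reached**

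With n = 20 and the 4-CR cut-off, power is 0.790 at a true rate of 25.5%, 0.804 at 26% and 0.893 at 30%. It equals 0.80 at 25.9%.

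**Step 5: the rate to be excluded**

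P(X ≥ 4 | 20, 0.10) = 0.133, against the 0.10 implied by a one-sided 90% interval. Exact one-sided coverage is 90.1% at a true 9%, 86.7% at 10% and 93.9% at 11%. This is the usual saw-tooth of an approximate interval with discrete data, and 10% falls in a dip.

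**The case against.** The arithmetic is not in dispute; its weight is. The strongest points on the other side are these.

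- **The gap is small and changes no decision.** Section 10.5.1 plans estimation only and sets no go/no-go rule, so 0.775 instead of 0.80 alters no analysis. That is true, and it limits the consequence. It does not make the stated figure right.
- **The plan says at least 25%, not exactly 25%.** Power is below 0.80 only for true rates between 25% and about 25.9%. But a power claim for a range has to hold at the bottom of the range, and there it does not.
- **The plan never calls its power exact.** Approximations fall on both sides of 0.80 (0.781 and 0.830), and 21 patients would give 0.808. A rounded planning figure is therefore plausible. Still, none of the formulas tried returns 0.80, and a figure given to two decimals should have been 0.77.
- **The analysed number may not be 20.** Section 7.8 replaces patients withdrawn in the first 3 months before their first post-therapy evaluation. Section 10.1 says that for patients who start therapy but do not reach the primary evaluation "their 6-month status will be treated as not achieving CR". If replaced patients stay in the denominator, it exceeds 20, and power at 25% becomes 0.808 for 21 patients but 0.677 for 22, where the cut-off rises to 5. This is a fair caution about the design. It does not rescue the 0.80, because both that figure and its correction are stated for 20 patients.
- **The 0.133 contradicts nothing in the plan.** Correct: the documents state no type I error. It is a matter of disclosure, and the power correction does not depend on it.

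**Conclusion.** The point holds. With 20 analysed patients and the interval section 10.8 specifies, exact power at a true CR rate of 25% is 0.775, which is 2.5 percentage points below the stated 0.80. The chance of missing the target is 0.225, not 0.20. The calculation assumes independent binomial responses and a denominator of exactly 20; all other inputs are the plan's own.

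The error is modest and does not undermine the design, but the figure is wrong in all three places and should be corrected. The 0.133 probability of excluding 10% when the true rate is 10% is normal behaviour for this kind of interval. It should be disclosed because 10% is the rate the trial sets out to exclude.

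**What to change.** In section 10.8, the synopsis and the schema, replace the power of 0.80 with: *exact power 0.77 at a true CR rate of 25% (the lower bound exceeds 10% when at least 4 of 20 patients have a CR)*.

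In section 10.8, add: *At a true CR rate of 10% the lower bound exceeds 10% with exact probability 0.13.*

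Sample size, endpoint and interval method need not change. The cost is wording in three places and slightly less favourable stated figures. In return the plan gives the responder cut-off, which currently appears nowhere.

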#### **10.9 Early Stopping Rules**

Early stopping rules will be performed after the first 10 patients have completed 3-month assessment for progression to T2 or greater stage based on TURBT samples. The study will not be halted while the early stopping rule is being evaluated.

If the probability of the 3-month progression rate being no higher than 20% is lower than 0.1, it will be considered as unacceptable and the study will be closed. Consequently, the trial would be stopped if 3-month progression is observed in 5 or more out of the first 10 patients. Note that the lower bounds of 90% Agresti-Coull confidence interval for 4, 5 and 6 out of 10 patients are 0.19, 0.27, and 0.35, respectively.

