## **8.5 Data and Safety Monitoring Plan**

As this is a small phase II trial of only 20 enrolled patients, a formal data and safety monitoring committee will not be employed. However, the Hoosier Cancer Research Network data management team provides patient safety oversight for all Hoosier Cancer Research Network trials. Specific data and safety monitoring tasks conducted by Hoosier Cancer Research Network include:

- Review of clinical trials conducted for progress and safety
- Review of all adverse events requiring expedited reporting as defined in the protocol
- Review of reports generated by data quality control review process
- Notification of the Sponsor Investigator and funding company of recommended action
- Notification of sites coordinated by Hoosier Cancer Research Network of adverse events requiring expedited reporting and subsequent committee recommendations for study modifications

In addition, Hoosier Cancer Research Network will compile data summary reports for this trial and submit these reports monthly to the Sponsor Investigator. Hoosier Cancer Research Network will submit data summary reports to a Data Safety Monitoring Committee (DSMC) a minimum of twice per year for review.

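### The 5-of-10 progression rule is read only once all ten 3-month results are in, with accrual running on; applying it as results arrive stops the same trials earlier, and the bounds quoted in its support do not match its 0.1 criterion

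*Combined protocol and SAP*

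**What the plan says.** Section 10.9 sets the criterion: "If the probability of the 3-month progression rate being no higher than 20% is lower than 0.1, it will be considered as unacceptable". The boundary follows: "Consequently, the trial would be stopped if 3-month progression is observed in 5 or more out of the first 10 patients". A note then gives the "lower bounds of 90% Agresti-Coull confidence interval for 4, 5 and 6 out of 10 patients are 0.19, 0.27, and 0.35, respectively".

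On timing: "Early stopping rules will be performed after the first 10 patients have completed 3-month assessment for progression to T2 or greater stage". The section adds that the study carries on during the evaluation. No section pauses enrollment between the tenth patient's entry and that patient's 3-month result.

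The section names no test, prior or sidedness for the 0.1 probability. Elsewhere, 10.8 says "The 6-month CR rate will be estimated with a one-sided 90% confidence interval of Agresti-Coull type", while 10.6.2 gives the muscle-invasive progression rate a 90% Agresti-Coull interval without calling it one-sided.

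On oversight, 8.5 says that "a formal data and safety monitoring committee will not be employed", and later in the same section sends data summaries to a Data Safety Monitoring Committee at least twice a year. Section 10.9 does not say who applies the rule.

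**The concern.** This is the only pre-set rule that closes the study, and it guards against progression to muscle-invasive disease. Two things weaken it.

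First, the count of progressions among the first ten can only rise. Once the fifth is recorded the decision is fixed, yet the rule waits for the remaining results while new patients enter. With a 3-month lag and only 20 patients, that wait covers a material part of the trial.

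Second, the criterion, the boundary and the supporting bounds do not come from one calculation. A reader cannot tell which one defines the rule, and no stopping probabilities are given by which to judge it.

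**Working it through.** **Inputs.** Criterion 0.1 against a 20% rate, boundary 5 of 10, one look after ten 3-month results (10.9). Total 20 patients, 12-month accrual (10.8); 18-month enrollment (synopsis). Uniform accrual is my assumption.

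**1. The quoted bounds.** The Agresti-Coull lower limit is p̃ − z·√(p̃(1 − p̃)/ñ), with ñ = n + z² and p̃ = (x + z²/2)/ñ.

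For x = 4, n = 10, z = 1.645: ñ = 12.706, p̃ = 0.4213, limit = 0.4213 − 1.645 × 0.1385 = 0.193.

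| Progressions of 10 | z = 1.645 (0.05 tail) | z = 1.2816 (0.10 tail) |
|---|---|---|
| 3 | 0.124 | 0.152 |
| 4 | 0.193 | 0.229 |
| 5 | 0.269 | 0.312 |
| 6 | 0.351 | 0.401 |

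The middle column reproduces the plan's 0.19, 0.27 and 0.35, so the note uses a 0.05 lower tail. At a 0.10 tail, 4 of 10 already excludes 20% (0.229).

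**2. What the 0.1 criterion gives under other methods.**

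| Method | At 4 of 10 | At 5 of 10 | Boundary |
|---|---|---|---|
| Exact binomial tail at 20% | 0.121 | 0.033 | 5 |
| One-sided 90% Clopper-Pearson lower limit | 0.188 | 0.267 | 5 |
| Posterior P(rate ≤ 20%), Beta(1,4) prior | 0.130 | 0.044 | 5 |
| Posterior, uniform prior | 0.050 | 0.012 | 4 |
| Posterior, Jeffreys prior | 0.066 | 0.015 | 4 |

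At 3 of 10 the uniform and Jeffreys posteriors are 0.161 and 0.205, so neither gives a boundary of 3.

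**3. Stopping probabilities of the stated rule.** P(X ≥ 5), n = 10, at true 3-month rates of 20, 30, 40 and 50%: 0.033, 0.150, 0.367 and 0.623.

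**4. Enrollment at the single look.**
- 12 months: 20/12 = 1.667 patients a month. The tenth enters at month 6 and is assessed at month 9; 1.667 × 9 = 15 enrolled.
- 18 months: 20/18 = 1.111 a month. The tenth enters at month 9 and is assessed at month 12; 1.111 × 12 = 13.3, so 13 enrolled.

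**5. The same boundary applied as results arrive.** Let k be the patient whose result is the fifth progression. The trial stops if k ≤ 10, which is the same event as five or more in ten. The set of stopped trials, and hence every probability in step 3, is unchanged.

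At a true rate of 40%, P(k) = C(k − 1, 4) × 0.4⁵ × 0.6^(k − 5):

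| k | 5 | 6 | 7 | 8 | 9 | 10 | Sum |
|---|---|---|---|---|---|---|---|
| P(k) | 0.0102 | 0.0307 | 0.0553 | 0.0774 | 0.0929 | 0.1003 | 0.3669 |

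Σ k·P(k) = 3.081, so the mean of k among stopped trials is 3.081/0.3669 = 8.4, against 10 for the single look: a saving of 1.6. During the 3-month lag, 5 more patients enter (12-month accrual) or 3 whole patients (18-month). Mean enrollment at closure is therefore 8.4 + 5 = 13.4 instead of 15, or 8.4 + 3 = 11.4 instead of 13.

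If five of the first six progress, closure comes no later than the sixth result: 11 enrolled instead of 15, or 9 instead of 13.

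**The case against.** A reader might infer that 5 of 10 is an error and that the 0.1 criterion requires 4. The documents do not support that. Section 10.9 names no method, and an exact one-sided binomial test at 0.1 gives exactly 5. The one-sided 90% Agresti-Coull form belongs to the complete response endpoint. For progression, 10.6.2 uses the same plain 90% wording as 10.9, and those limits (0.193 at 4, 0.269 at 5) are consistent with a boundary of 5. Posterior readings depend on the prior. Moving to 4 would also be a trade-off: stopping probability at a true 20% rate would rise from 0.033 to 0.121, against a rise from 0.367 to 0.618 at 40%. This objection stands, and the boundary should not be called wrong. What remains is that a 0.05-tail note sits beside a 0.1 criterion and that the calculation supporting 5 is not stated.

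On timing, the single look is openly stated and the saving is modest: 1.6 patients in stopped trials, or 0.367 × 1.6 = 0.6 averaged over all trials at a 40% rate. Nor may one infer that the study could not close sooner. Section 4.3 allows termination at any time for any reason, and 8.5 gives the sponsor investigator monthly summaries. These are discretionary safeguards. They do not explain why a pre-set rule should wait once its outcome is certain, and the change costs nothing in error rates.

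**Conclusion.** The timing point holds. The rule is read later than it needs to be, with about 13 to 15 of 20 patients enrolled, and applying the same boundary sequentially closes the same trials with fewer patients entered. The size is small to moderate: 1.6 patients on average in trials that stop at a true 40% rate, and more when progressions cluster early. This rests on uniform accrual, no withdrawals before month 3 and results available at 3 months. If the tenth assessment falls 7 days late, the counts at the look become 15.4 and 13.6.

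The inconsistency in the justification also holds, as a matter of specification: the 0.1 criterion, the 5-of-10 boundary and the quoted bounds do not share one calculation. The boundary itself is defensible. Section 8.5 contradicts itself on whether a monitoring committee has a role.

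**What to change.** In 10.9:
- Keep the boundary of 5. Apply it as each 3-month result among the first ten arrives, and close accrual as soon as the fifth progression is recorded.
- Define the criterion as an exact one-sided binomial test of a 20% rate at 0.1, giving the tails 0.121 at 4 and 0.033 at 5.
- Label the quoted bounds as two-sided 90% Agresti-Coull limits with a 0.05 tail, or replace them with figures from the named test.
- State the stopping probabilities: 0.033, 0.15, 0.37 and 0.62 at true rates of 20, 30, 40 and 50%.

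Reconcile the committee statements in 8.5 and say in 10.9 who applies the rule. The 12-month accrual in 10.8 and the 18 months in the synopsis should also be made to agree, since enrollment at the look depends on them.

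The cost is wording, plus prompt reporting of each of the first ten 3-month results to whoever applies the rule. There is no change in sample size or in the chance of stopping at any true rate.

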## **11 Ethical Considerations and Administrative Procedures**

### **11.1 Regulatory and Ethical Compliance**

This clinical study was designed, shall be implemented and reported in accordance with the ICH Harmonized Tripartite Guidelines for Good Clinical Practice, with applicable local regulations (including European Directive 2001/20/EC and US Code of Federal Regulations Title 21), and with the ethical principles laid down in the Declaration of Helsinki.

### **11.2 Responsibilities of the Investigator and IRB/IEC/REB**

The protocol and the proposed informed consent form must be reviewed and approved by a properly constituted Institutional Review Board/Independent Ethics Committee/Research Ethics Board (IRB/IEC/REB) before study start. A signed and dated statement that the protocol and informed consent have been approved by the IRB/IEC/REB must be given to Novartis before study initiation. Prior to study start, the investigator is required to sign a protocol signature page confirming his/her agreement to conduct the study in accordance with these documents and all of the instructions and procedures found in this protocol and to give access to all relevant data and records to Novartis monitors, auditors, Novartis Clinical Quality Assurance representatives, designated agents of Novartis, IRBs/IECs/REBs and regulatory authorities as required.

### **11.3 Informed Consent Procedures**

Eligible patients may only be included in the study after providing written (witnessed, where required by law or regulation), IRB/IEC/REB-approved informed consent <if applicable: or, if incapable of doing so, after such consent has been provided by a legally acceptable representative of the patient. In cases where the patient's representative gives consent, the patient should be informed about the study to the extent possible given his/her understanding. If the patient is capable of doing so, he/she should indicate assent by personally signing and dating the written informed consent document or a separate assent form>. Informed consent must be obtained before conducting any study-specific procedures (i.e. all of the procedures described in the protocol). The process of obtaining informed consent should be documented in the patient source documents.

Novartis will provide investigators in a separate document with a proposed informed consent form (ICF) that is considered appropriate for this study and complies with the ICH GCP guideline and regulatory requirements. Any changes to this ICF suggested by the investigator must be agreed to by Novartis before submission to the IRB/IEC/REB, and a copy of the approved version must be provided to the Novartis monitor after IRB/IEC/REB approval.

Women of child bearing potential should be informed that taking the study medication may involve unknown risks to the fetus if pregnancy were to occur during the study and agree that in order to participate in the study they must adhere to the contraception requirement for the duration of the study. If there is any question that the patient will not reliably comply, they should not be entered in the study.

This study will include requesting patient consent to keep and store any leftover tissue samples in the Hoosier Cancer Research Network already established Biorepository for possible future IRB approved research.

